## 1 OBJECTIVES

### 1.1 Primary

The goal of this descriptive (not definitive) study is to study an adequate number of subjects to evaluate the impact of MRI magnet field strength (3T versus 7T), contrast agent (ferumoxytol and gadolinium), tumor size, and tumor permeability on a series of imaging measures to monitor and evaluate tumor characteristics.

Following are the specific objectives for this study:

1.1.1 Primary Aim 1: To compare quantitative blood brain barrier permeability measurements ( $K^{trans}$ ) of a standard gadolinium (Gd) MRI contrast agent at 3 T and 7 T using dynamic contrast enhancement (DCE) MRI.

We hypothesize that contrast agent detection sensitivity is improved at 7 T compared to 3 T, allowing the construction of  $K^{trans}$  parametric maps with higher precision. The primary outcome measure for these analyses will be  $T_1$ -weighted image contrast to noise ratio (CNR), calculated as the signal increase caused by the Gd agent divided by background noise.

1.1.2 Primary Aim 2: To compare dynamic susceptibility contrast (DSC) based perfusion measures at 3 T and 7 T.

We hypothesize that due to increased  $T_2^*$  susceptibility effects the 7 T images will provide a higher CNR compared to 3 T images. The primary outcome measure for these analyses will be the CNR, calculated as the signal intensity decrease caused by the Ferumoxytol bolus, divided by the background noise.

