### 1.2 Secondary

1.2.1 To describe the blood brain barrier permeability to Ferumoxytol and to a standard gadolinium-based MRI contrast agent using signal intensity changes as described above.

1.2.2 To describe cerebral blood volume (CBV) measurements obtained using a standard gadolinium MRI contrast agent and ferumoxytol. CBV will be quantified using dynamic susceptibility contrast (DSC) techniques with Gd or Ferumoxytol contrast agents. The use of DSC techniques with standard Gd MRI contrast agents in tumors with leaky blood vessels can lead to inaccurate CBV estimates because of Gd extravasation. We expect to obtain lower blood volume estimates with ferumoxytol than with gadolinium in leaky tumors. We do not expect significant differences in less leaky tumors.

1.2.3 To evaluate tumor microvascularity on susceptibility-weighted images (SWI). The susceptibility weighted images will be acquired before and after ferumoxytol administration to investigate blood vessel visibility within the tumor bed. Morphological and caliber differences of intratumoral vessels in comparison to normal cortical penetrating vessels will be analyzed.

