### **7.3 Vascular Permeability measurement**

$T_1$  weighted MR data will be collected before and after contrast agent administration. Permeability will be evaluated by applying dynamic contrast enhanced (DCE) scans for quantitative  $T_1$  measurements 4 times over 45 minutes and also 24±6 hours after contrast administration. Using the  $R_1$  ( $=1/T_1$ ) values,  $K^{trans}$  will can be calculated in the selected ROIs, (i. tumor core, ii. tumor rim, iii. ipsilateral control region iv. contralateral control region).

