and field strength (3T and 7T). Each subject will contribute one measure for each combination of imaging agent and field strength (4 measures total). This will not be a definitive analysis as the power cannot be determined *a priori*. The mixed model allows for estimation of the means and confidence intervals for imaging agent and field strength (57). These data will be used to plan future comparative studies. For the second Secondary Aim, blood volumes will be compared using repeated measures ANOVA to compare the imaging agents. For the third Secondary Aim, analyses will add covariates of prior therapy to the analyses listed above. For the comparisons between treated and untreated subjects, means and confidence intervals will be estimated for each group for the perfusion and permeability measures and for the baseline characteristics listed above. Since prior treatment is likely confounded with other variables (e.g. disease severity), these comparisons will also be descriptive in nature and mainly be used to plan future studies.

For Secondary Aim five, the pathology will be analyzed qualitatively for the presence of iron staining. The amount and localization of the staining will be assessed, with attention paid to whether the tumor cells themselves or reactive cells in and around the tumor demonstrate iron uptake.

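### The blood-volume analysis in Section 9.3 compares the two agents overall and, as written, does not examine the dependence on tumor leakiness that objective 1.2.2 expects

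*Combined protocol and SAP*

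**What the plan says.** Objective 1.2.2 is worded as a description: "To describe cerebral blood volume (CBV) measurements obtained using a standard gadolinium MRI contrast agent and ferumoxytol". It explains that gadolinium escaping from leaky vessels distorts CBV, and then states two expectations: "We expect to obtain lower blood volume estimates with ferumoxytol than with gadolinium in leaky tumors" and "We do not expect significant differences in less leaky tumors". The overall goal in Section 1.1 also covers the influence of "contrast agent (ferumoxytol and gadolinium), tumor size, and tumor permeability on a series of imaging measures".

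The analysis of this aim in Section 9.3 is one sentence: "blood volumes will be compared using repeated measures ANOVA to compare the imaging agents". Imaging agent is the only factor named. Under the third Secondary Aim, "analyses will add covariates of prior therapy to the analyses listed above".

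Section 7.3 plans Ktrans in four regions: "i. tumor core, ii. tumor rim, iii. ipsilateral control region iv. contralateral control region". Section 7.5 lists the same four and says they are those used for perfusion. In Section 6.1 the Day 1 gadolinium perfusion series and the T1 series for permeability follow the same injection.

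**The concern.** The expectation attached to 1.2.2 is that the agent difference changes with leakiness. The planned comparison estimates one agent difference averaged over everyone enrolled. Section 3.1 admits primary and metastatic tumors at any stage of treatment, and the strata in Section 5.2.3 are tumor type and prior treatment. The share of leaky tumors is therefore left to chance.

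Two readings of the result would then be unsafe. An overall difference would not show that leakage is the reason for it. A small overall difference would not show that the agents agree where leakage is low. Section 9.3 says the results are meant for planning later definitive studies, and a difference averaged over an arbitrary case mix is a weak planning input.

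**Working it through.** **No figure to reproduce.** The documents give no effect size, SD, alpha or power for the CBV comparison, and Section 9.4 disclaims any statistical basis for the 150 subjects. The check is therefore of the text, followed by an illustration on assumed inputs.

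**Could a leakiness term enter from elsewhere?**

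- Third Secondary Aim (9.3): adds prior therapy only.
- Section 9.2: permeability appears as a baseline summary.
- Section 9.3, opening: allows optional control for further parameters, none of them named.
- Section 9.3, Primary Aims: baseline variables can enter as covariates under a p<0.10 rule. This is written for the primary analyses.
- Section 2.3 and Table 1: describe comparing the gadolinium partition coefficient with CBV to gauge leakage. Section 9.3 does not take this up.

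At most, these routes give a main effect of permeability. A main effect shifts the CBV of both agents by the same amount and cancels in the within-subject difference. Only an agent-by-permeability term bears on the expectation in 1.2.2.

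**What the overall comparison estimates.** Let y be gadolinium minus ferumoxytol CBV within a subject, with SD 1 (assumed). Let p be the leaky share, and dL and dN the mean of y in leaky and less leaky tumors. Then

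overall difference = p × dL + (1 − p) × dN.

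Take p = 0.5 and N = 120 (150 less the 20% crossover allowance of Section 5.6). The rejection rates are from 5,000 simulated trials, two-sided 5%.

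| Pattern | dL | dN | Overall difference | Overall test rejects | Leaky vs less leaky contrast rejects |
|---|---|---|---|---|---|
| As 1.2.2 expects | 0.5 | 0 | 0.5×0.5 + 0.5×0 = 0.25 | 75% | 76% |
| Uniform | 0.25 | 0.25 | 0.5×0.25 + 0.5×0.25 = 0.25 | 78% | 5% |
| Reversed | 0 | 0.5 | 0.5×0 + 0.5×0.5 = 0.25 | 77% | 78% |

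The overall comparison looks the same in all three. The contrast separates the uniform pattern from the other two by its rejection rate, and those two from each other by its sign.

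**Case mix.** With dL = 0.5 and dN = 0, the overall difference is 0.3 × 0.5 = 0.15, 0.5 × 0.5 = 0.25 or 0.7 × 0.5 = 0.35 SD at leaky shares of 30%, 50% or 70%.

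**What a leakiness contrast could deliver.** Approximate power is Φ(d / √(1/nL + 1/nN) − 1.96), where nL and nN are the numbers of leaky and less leaky tumors. With N = 120, d = 0.5 and p = 0.5, √(1/60 + 1/60) = 0.183, 0.5/0.183 = 2.74, and power is 78%. At p = 0.3 or 0.7 it is 71%.

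The range over sample size, for d = 0.5, is 63–71% at N = 100 (125 less 20%) and 80–87% at N = 150. Over effect size, at N = 120, it is about 33–38% for d = 0.3 and 94–97% for d = 0.7.

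The 95% CI half-width for the agent difference in less leaky tumors at N = 120 is 1.96/√84 = 0.21, 1.96/√60 = 0.25 and 1.96/√36 = 0.33 SD at leaky shares of 30%, 50% and 70%.

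The split into two groups is only for the illustration. The analysis proposed below keeps Ktrans continuous.

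**The case against.** The best defence is that 1.2.2 undertakes to describe. Its leakiness sentences are expectations, whereas the Primary Aims in Section 1.1 state hypotheses. Section 9.3 labels every analysis descriptive, and Section 9.5 calls the study exploratory. An overall agent comparison does serve the literal objective. This stands, and it limits the weight of the point. It does not remove it, because a descriptive estimate of the agent difference by leakiness is what the stated expectation calls for.

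Several stronger readings are tempting, but the documents do not support them:

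- **The trial cannot answer the question.** Ktrans is planned in the same subjects and regions, so the limit is in the analysis text.
- **A single overall comparison is all that is planned.** Prior therapy is added under the third Secondary Aim, and Section 2.3 describes a leakage comparison. Section 9.3 also does not say that tumors are pooled; this is inferred from the absence of any stratifier.
- **Less leaky tumors would be credited with a false difference.** The main effect assigns no value to that group. Only a misreading of it would.
- **The dilution has a known size.** Leaky share, effect and SD are all assumed above.
- **The partition coefficient would give a leakiness measure free of shared error.** It uses T1 changes after the same Day 1 gadolinium injection as Ktrans. It also needs a blood-pool value, which the regions in Section 7.3 do not include.

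**Conclusion.** The point holds in a limited form. As written, Section 9.3 does not examine the leakiness expectation in 1.2.2, and nothing elsewhere in the plan supplies the missing term. That conclusion rests on the text alone. The overall agent difference cannot distinguish the expected pattern from a uniform or reversed one. This follows from the averaging formula for any mix of tumors, but how far the estimate is diluted cannot be stated from the documents.

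The power and interval figures are illustrations. They assume a common SD for the within-subject difference, a two-group split, and leaky shares of 30–70%.

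This is a worthwhile and cheap improvement to one secondary aim. No primary result or safety conclusion depends on it.

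**What to change.** In Section 9.3, for the second Secondary Aim:

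1. Add continuous Day 1 gadolinium Ktrans, taken in the same tumor region as the CBV value, and its interaction with agent to the repeated measures model. Name the region in advance.
2. Include the actual field strength of each scan as a factor, or restrict the analysis to subjects with both dynamic sessions on the same magnet. Section 5.3.4 keeps Day 2 on the Day 1 scanner, but Section 5.6 allows a one-day crossover. Assigned field strength would then be wrong for one of the two scans. The crossover exclusion in 9.3 is written for the primary analyses.
3. Report the interaction slope, and the gadolinium-minus-ferumoxytol CBV difference with 95% CI at stated low and high Ktrans levels (for example, levels representing the lowest and highest thirds).
4. Judge agreement in less leaky tumors by that interval, not by non-significance.
5. State as a limitation that Ktrans and gadolinium CBV come from the same gadolinium session, so part of their association may be shared error.

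The cost is analysis wording and a slightly larger model, using measurements already planned. The interaction is estimated less precisely than the main effect. In the illustration at N = 120 with an even split, its standard error is √(1/60 + 1/60) = 0.183 SD, against 1/√120 = 0.091 SD for the overall difference, about double. The overall agent comparison can still be reported beside it.

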**5.3.4 Day 2**

Imaging

- Anatomical imaging on 3T & 7T and dynamic MRI (with ferumoxytol, see section 4.2). A subset of 25 of the 150 subjects will only undergo MRIs on the 7T magnet.
- Dynamic imaging will be performed on the same scanner as on which the dynamic the dynamic imaging was acquired on Day 1(as described below on Section: 6.0). Ferumoxytol Administration:
  - The ferumoxytol will be diluted 1:2 to make a 10mg/ml solution. The dose of ferumoxytol will be 4 mg/kg (to a maximum of 510 mg), and will be administered intravenously on day 2.
  - Dose 1: Give 1/4th of the total dose (1mg/kg); inject at up to 3 ml/sec followed by a saline flush. This rate is required for adequate signal change during the dynamic imaging.
  - Dose 2: Give 3/4th of the total dose (3mg/kg); inject no faster than 1 ml/sec and followed by a saline flush
  - 
  - The dilution and injection parameters of the ferumoxytol may be adjusted to obtain optimal signal changes on MRI/MRA and to decrease the possibility of an allergic reaction. Injection rate can be varied based on the participant's IV site, but the total dose will never exceed 510mg.

Monitoring

- A clinical examination will be performed before and after the MRI session on Day 2.. Blood pressure and pulse will be monitored before the first dose of ferumoxytol and after each dose of ferumoxytol, and at 30 minutes after the initial dose of ferumoxytol.

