#### **5.6 Subject Evaluability**

Subjects who are assigned to either the 3T or the 7T magnet strength MRI instruments may not be able to complete the imaging on the assigned strength on a given day. This will most likely be due to an MRI technical issue on the day the subject has been assigned. The 7T MRI is more likely to experience technical difficulties as this is a research instrument and is not a standard clinical product. In addition, a few subjects may not be able to tolerate an MRI examination on a particular day. If one MRI instrument is unavailable and the other one is available, the subject will be "crossed-over" for that day. For Primary Aims 1 and 2, crossing a subject on either day 1 or day 2 (but not both) will mean that the subject will be evaluable for one aim (corresponding to the non-crossover day) but not for the other. The sample size is adequate to allow up to 20% of subjects to be crossed over on at least one day. If one MRI instrument is not available on Study Day 3, data will be collected from that subject on only one instrument and these data will be used only to describe the range of values for that magnet strength.

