### **9.3 Descriptive Statistical Analyses**

All analyses described are viewed as descriptive in nature to better understand the variation in these parameters and not to provide definitive results as would be expected in a Phase III trial. The statistical analyses provide appropriate frameworks for assessing the relative magnitudes of effects while potentially controlling for other parameters of interest. Results will be used to plan for future definitive studies of the parameters that have appropriate power calculations and sample sizes. These analyses will be performed when target sample sizes are achieved and not on as interim analyses.

For Primary Aim 1, the primary descriptive comparisons are paired sample t-tests comparing the normalized signal intensity changes (CNR) for T1-weighted MRI signal at 3T and at 7T. Secondary analyses will use a repeated measures analysis of variance (ANOVA) model to compare 3T and 7T while adjusting for other factors including tumor type, prior therapy, and, potentially, important baseline factors that differ between the subjects assigned to the two field strengths. These tests are descriptive in nature and are not powered to provide a complete answer. Subjects who are scheduled to be imaged by a magnet of one field strength but are “crossed-over” to the other magnet or who otherwise fail to complete the scheduled imaging will not be included in these analyses. For the baseline characteristics, if two-sample tests of hypotheses indicate a significant difference ( $p<0.10$ ) between 3T and 7T signal intensity changes for a particular variable, that variable will be included in the ANOVA model as a covariate. Normality will be assessed graphically and, if needed, a transformation (e.g. the logarithmic transform) will be applied. These analyses will be performed for Gd T1-weighted MRI data only

For Primary Aim 2, the analyses will be similar to those for Aim 1 above using normalized (CNR) signal intensity decreases in the DSC data sets. . The same factors and analyses will be used. This objective assesses only Ferumoxytol.

For the first Secondary Aim, mixed model repeated measures ANOVA's will be fit. The outcomes will be relevant dynamic MRI (DCE and DSC) signal intensity changes for permeability and for perfusion. Factors will include imaging agent (Gd or ferumoxytol)

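### A one-day crossover puts the two contrast agents on different field strengths, and the blood-volume comparison in 9.3 names no field term and no rule for these subjects

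*Combined protocol and SAP*

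**What the plan says.** Objective 1.2.2 describes CBV from DSC imaging with each agent. It expects lower values with ferumoxytol than with gadolinium in leaky tumors and no marked difference in less leaky ones. Gadolinium is given on Day 1 (4.1) and ferumoxytol on Day 2 (4.2, 5.3.4). Section 6.1 assigns the DSC series to one field per subject. For Day 2, section 5.3.4 states: "Dynamic imaging will be performed on the same scanner as on which the dynamic" imaging of Day 1 was acquired.

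Section 5.6 provides for outages: "If one MRI instrument is unavailable and the other one is available, the subject will be" crossed over for that day. It gives the consequence for two aims only: "For Primary Aims 1 and 2, crossing a subject on either day 1 or day 2 (but not both) will mean that the subject" counts for one aim and not the other. It adds: "The sample size is adequate to allow up to 20% of subjects to be crossed over on at least one day".

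In 9.3 the exclusion of crossed-over subjects, and of those "or who otherwise fail to complete the scheduled imaging will not be included in these analyses", stands in the Primary Aim 1 paragraph. Primary Aim 2 takes it over because its analyses are described as similar. For the first Secondary Aim the factors are imaging agent "and field strength (3T and 7T). Each subject will contribute one measure for each combination of imaging agent and field strength (4 measures total"). For the second, the whole specification is that "blood volumes will be compared using repeated measures ANOVA to compare the imaging agents".

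**The concern.** The within-subject agent comparison is clean only when both DSC scans are at the same field. A subject crossed over on one day has gadolinium CBV at one field and ferumoxytol CBV at the other, so agent and field cannot be separated in that subject. No evaluability rule or exclusion covers this for CBV, and no field term is named to absorb it.

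A field effect is plausible. Primary Aim 2 hypothesises a higher DSC contrast-to-noise ratio at 7T, and the acquisition settings in 6.3 differ between the scanners. Objective 1.2.2 makes a directional prediction, and 9.3 says the results will be used to plan definitive studies. An agent difference or standard deviation distorted by mixed-field pairs would carry into that planning.

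**Working it through.** The plan has no figure to reproduce: 9.4 says the sample size of 150 has no statistical justification, and no effect size or SD is given for CBV.

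**Model.** For each subject let d = CBV(ferumoxytol) − CBV(Gd) = A + δ·f + error. A is the agent effect. δ is the field effect (7T minus 3T), taken as the same for both agents. f = 0 if both scans are at one field, +1 for Gd at 3T with ferumoxytol at 7T, and −1 for Gd at 7T with ferumoxytol at 3T. With agent as the only factor, the estimate is the mean of d, so

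bias = δ × (p[+1] − p[−1]).

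**Share of mixed-field subjects.** The ceiling in 5.6 is 20% crossed on at least one day. The 25 subjects in the 7T-only subset (5.1) cannot cross, which leaves 150 − 25 = 125.
- 20% of 125 = 25 subjects. This is 25/125 = 20% if the subset is left out of the CBV comparison, and 25/150 = 16.7% if it is included.
- 20% of all 150 = 30 subjects, or 30/150 = 20%.

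Subjects crossed on both days count toward the 20% but keep both agents on one field, so 17-20% is an upper limit.

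**Bias at a 20% share.**
- Directions equal: 0.
- 75/25 split: 0.20 × (0.25 − 0.75) × δ = −0.10δ.
- All with Gd at 7T and ferumoxytol at 3T: −0.20δ.

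If δ were 10-30 percentage points (an assumption), the one-way limit would be 0.20 × (10 to 30) = 2 to 6 points, or 0.167 × (10 to 30) = 1.7 to 5.0 points at the lower share.

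**Noise when directions balance.** The variance of d becomes σ² + 0.20·δ². Base SDs of 20 and 30 points are assumed.
- σ = 30: √(900 + 20) − 30 = 0.3 for δ = 10; √(900 + 180) − 30 = 2.9 for δ = 30.
- σ = 20: √(400 + 20) − 20 = 0.5; √(400 + 180) − 20 = 4.1.

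The SD therefore rises by about 0.3 to 4 points.

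**Simulation.** N = 150, 4,000 runs per setting, A = 0, two-sided 5% test for illustration, δ in units of the SD of d. False-positive rate of the agent-only analysis:

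| Mixed-field subjects | Direction split | δ = 0.5 SD | δ = 1.0 SD |
|---|---|---|---|
| 30 | 50/50 | 4.2% | 3.1% |
| 30 | 75/25 | 7.8% | 15.6% |
| 30 | 100/0 | 21.4% | 61.9% |
| 25 | 100/0 | 16.2% | 46.8% |

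With a field term, or with mixed-field subjects excluded, the bias is about zero and the rate is 4.5-5.5% in every setting. With 30 such subjects the standard error, in SD units, is 0.081-0.082 for agent only, 0.082-0.091 with a field term, and 0.091-0.092 with exclusion.

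**The case against.** The sentence in 9.3 is a one-line summary. It does not say that agent is the only model term, and 9.3 speaks generally of possibly controlling for other parameters of interest. This stands: the plan is silent on a field term and does not rule one out. But the first Secondary Aim, in the same section, does name field, so an analyst following the text would fit agent alone for CBV.

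The one-way case is extreme, and this also stands. With balanced assignment, about 125/2 = 62 of the two-field subjects would be assigned to 7T. For all 25 crossovers to be 7T failures on Day 2, about 25/62 = 40% of them would have to cross that day and none from 3T. Section 9.5 expects the 7T proportion to be only somewhat higher. Day 1 crossovers from 7T followed by a return to 7T run the opposite way and partly cancel. Cancellation cannot be assumed, though. If the same-scanner rule is obeyed after a Day 1 crossover, only Day 2 crossovers mix fields, and since 7T fails more often these would mostly be Gd at 7T with ferumoxytol at 3T.

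Normalisation may shrink the field effect: Table 1 normalises CBV by the arterial input, and 7.2.2 normalises rCBV by a control region. Nothing in the documents shows that it removes the effect. The 3T list in 6.3 does not label either candidate sequence as DSC, and the settings are subject to change, so the difference in parameters only makes a field effect plausible.

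Finally, the aim is secondary and every analysis is called descriptive. That limits the severity but does not remove the gap.

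**Conclusion.** The concern holds as a gap in specification. In each mixed-field subject the agent contrast absorbs the whole field difference, and neither a rule nor a named model term prevents it. The bias in the mean is at most about 17-20% of the field effect and is zero if directions balance; in that case only noise is added, in quadrature. The figures in points and SD units rest on assumed field effects and base SDs, and on a field effect that is the same for both agents.

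A reader might infer that the CBV comparison will be materially biased, or that the crossovers add the full √0.20 × (10 to 30) = 4 to 13 points to the SD. The documents support neither. They give no field effect on CBV, the 20% is a ceiling that includes subjects crossed on both days, and that SD component combines with the base SD as variances do. A reader might also infer that mixed-field subjects must be dropped. A field term removes the bias just as well and keeps them. This is a moderate point, to be settled before analysis.

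**What to change.** - **9.3, second Secondary Aim:** add the actual field strength of each DSC acquisition as a factor in the CBV model. Report same-field pairs only as a sensitivity analysis.
- **5.6:** state how a one-day crossover is handled for the within-subject agent comparison. A subject crossed on both days still has a same-field pair and should be treated as such.
- **5.6 and 5.3.4:** reconcile crossover for a single day with the same-scanner requirement, so that it is clear which subjects can have mixed-field pairs.

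The cost is a few sentences, one model term, and a standard error of 0.082-0.091 SD against 0.081-0.082 for agent only (30 mixed-field subjects). No additional scans are needed and no subject leaves the main analysis. The sensitivity analysis would use 120 of 150 subjects with 30 mixed-field pairs, or 125 of 150 with 25.
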